	
 • Open, prospective, observational study (PMS study) in accordance with section 4(23) and section 67(6) AMG: all enrolled AF patients will be observed over 12 months during treatment with dabigatran etexilate or VKA. • In this NIS, information about dabigatran etexilate/VKA persistence and adherence will be collected in 4000 AF patients. 
Visit 1 (start of observation)
 
 • Patient data: sociodemographic data (sex, age, height, weight, education, marital status, health insurance status) • Case history of non-valvular atrial fibrillation (AF): disease onset, data on disease severity (individual components of the CHA₂DS₂-VASc score) and bleeding risk (individual components of the HAS-BLED score) • Start of treatment with dabigatran etexilate (110 or 150 mg hard capsules) or VKA (start date) • Concomitant medication: antiarrhythmics, antihypertensives, lipid-lowering agents, other prescription-only medicines

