The analysis is performed on the basis of the patient cohorts resulting from the 1:1 matching. Kaplan Meier estimates for the time to discontinuation of treatment (cf. definition in section 5.1.) will be calculated separately for the dabigatran and the VKA patient group and illustrated graphically. In particular, the Kaplan Meier estimates for persistence at time 3, 6, 9 and 12 months will be reported. The comparison in terms of the persistence of patients on treatment with dabigatran versus VKA will be performed by means of the stratified log-rank test, which takes account of the dependency of treatment groups resulting from matching (cf. Klein, Moeschberger, 1997, ²²). Patients who discontinued the study prematurely and for whom no treatment discontinuation is documented will be censored at the time of study discontinuation. Patients who end the study as planned will be censored on the day after the last visit if no previous treatment discontinuation is documented.

The absolute number and proportion of patients discontinuing the initial treatment in the course of the study will be summarised overall and according to the reasons for discontinuation for the dabigatran and VKA cohorts.

The association of patient characteristics (including treatment allocation) with persistence will be investigated by means of Cox regression models (univariate and multivariate models). Baseline characteristics will be presented stratified for patients who discontinue the treatment in the course of the study and those who do not.

A multivariable Cox regression model (including the factors used for calculating the PS and choice of treatment) will be reported as a sensitivity analysis. For this analysis, all patients who are within the common supports of the empirical density function of the PS (instead of matched pairs) will be included; the common support is determined after excluding patients with a propensity score above the 97.5% percentile and below the 2.5% percentile in each treatment group in order to avoid a strong influence from patients with extreme PS values.

Adherence

The analysis is performed on the basis of the patient cohort resulting from 1:1 matching. The Morisky questionnaire consists of 8 questions and will be presented at the time of the 6-month visit. The analysis and categorisation of patients into the categories

- poor adherence (score >2)
- medium adherence (score=1, 2) and
- high adherence (score=0)

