is performed according to Morisky. For patients who have not answered one or more questions, this score is not calculated. If the proportion of patients with missing answers is high (e.g. >20%), a sensitivity analysis will be performed, in which the score will also be

calculated if up to 2 questions per patient are missing²³. Patients who at the time of the visit are no longer on the initial therapy and those who have already discontinued the study before this time will be described separately from those for whom the Morisky score cannot be calculated for other reasons. Patients with missing values are analysed in terms of their baseline characteristics in comparison with patients with an evaluable Morisky score; patients with missing values will be stratified into the above-mentioned groups of study drop-outs, treatment drop-outs and patients with missing values for other reasons and the analysis will only be performed for strata with at least 200 patients (total and per treatment group).

The number and proportion of patients who fall into the different adherence classes will be presented for the dabigatran and VKA patients.

Coding

The current version of the Medical Dictionary for Drug Regulatory Activities will be used for coding adverse events. Concomitant medication will be coded using the current version of the WHO-DD.

Analysis of safety endpoints

For the analysis of adverse events, all patients documented in the CRF with at least one prescription for dabigatran etexilate or VKA will be included. Analyses of adverse events are descriptive and will be performed in accordance with Boehringer Ingelheim standards. In the analysis of adverse events, the focus is on treatment-emergent events. Events that occur in the period between the start of treatment and the permanent discontinuation of treatment or the end of the study (in patients in whom no permanent discontinuation of the medication is documented in the course of the study) + 6 days are categorised as treatment emergent and will be presented in frequency tables for dabigatran and VKA patients.

Adverse events that occur before or after this period will be assigned to “screening” or “post-treatment” and only presented in listings.

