3. INTRODUCTION

As per ICH E9, the purpose of this document is to provide a more technical and detailed elaboration of the principal features of the analysis described in the protocol, and to include detailed procedures for executing the statistical analysis of the primary and secondary variables and other data.

This TSAP assumes familiarity with the Clinical Trial Protocol (CTP), including Protocol Amendments. In particular, the TSAP is based on the planned analysis specification as written in CTP Section 7 "Statistical Analysis". Therefore, TSAP readers may consult the CTP for more background information on the study, e.g., on study objectives, study design and population, treatments, definition of measurements and variables, planning of sample size, randomization.

SAS® Version 9.3 or higher will be used for all analyses.

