4. CHANGES IN THE PLANNED ANALYSIS OF THE STUDY

None.

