7.4 PRIMARY ENDPOINT(S)

The analysis of the primary endpoint will be based on the patient cohort resulting from the 1:1 matching. Time until termination of treatment will be presented for both treatment groups (Dabigatran etexilate vs. VKA) by Kaplan-Meier estimates and displayed graphically, respectively. Especially for time points 3, 6, 9 and 12 months Kaplan-Meier estimates for persistence will be calculated.

The comparison of persistence between the treatments with dabigatran etexilate versus VKA will be conducted by means of the stratified Log-rank test, which takes dependencies resulting from the matching of the treatment groups into account. Patients who discontinue

study prematurely and without documented treatment discontinuation will be censored at study termination. Patients completing the study as planned will be censored at the day after last visit, if no earlier treatment discontinuation is documented. Association between patient characteristics (incl. method of treatment) and persistence will be determined by means of cox regression (univariate and multivariate model). First, univariate regression for each of the independent variables will be performed. Afterwards, all covariates will be entered into a stepwise multivariate regression. The entry level will be $p=0.5$ and the stay level $p=0.1$. Baseline characteristics will be presented stratified by patients who discontinued the study prematurely versus no discontinuation.

A multivariate Cox Regression model (including factors for the calculation of the propensity score and the choice of treatment) will be used as sensitivity analysis. All patients, who are within the “common support” of the empiric PS density function (instead of the matched pairs), will be included in this analysis. The “common support” will be determined after patients with a propensity score above the 97.5% percentile and below the 2.5% percentile have been excluded for each treatment group, respectively. This will be done to avoid high influence of patients with extreme PS.

The following covariates will be used –depending on the sample size- for the Propensity Score Matching and the sensitivity analysis

- CHA₂DS₂-VASC Score (<2, ≥ 2)
- HAS BLED-Score (<3, ≥ 3)
- Age at registration (<65, 65-<75, ≥ 75)
- Previous stroke (Yes, No)
- Treatment (VKA, Pradaxa[®]) (sensitivity analysis only)

and the following covariates will be used –depending on the sample size- for the Cox regression

- CHA₂DS₂-VASC Score (<2, ≥ 2)

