7.5 SECONDARY ENDPOINT(S)

Absolute number and percentage of patients, who discontinue the initial treatment during study, will be summarized collectively and according to reasons for discontinuation for the dabigatran etexilate and VKA cohort, respectively.

The analysis of secondary endpoints will be based on the patient cohort resulting from the 1:1 matching.

The Morisky questionnaire consists of 8 question and will be answered at the 6- months visit. Each question can be scored with 0 or 1. For questions 1-7, 'no' will be scored with 0 and 'yes' with 1. For question 8, 'None/rarely' will be scored with 0 and all other answers with 1. The Morisky score is given by the sum of the values of each question, which implies a score between 0 and 8.

The categorisation of patients into low adherence (score >2), medium adherence (score=1,2) and high adherence (score=0) is done according to Morisky. The score will only be calculated for patients who answered all eight questions. In case that the proportion of the patients who did not answers all questions is too high (i.e. >20%) a sensitivity analysis will be conducted in which the score will be calculated if up to 2 questions per patient are missing. Patients who changed their initial treatment or withdrew from the study before the 6-months visit, will be displayed seperately from those for which the Morisky score could not be calculated for other reasons. Patients with missing data will be analyzed regarding to their baseline characteristics in comparision to the patients with an evaluable Morisky score; patients with missing values at the 6-months visit will be stratified into (i) the groups of study drop-outs, (ii) treatment drop-outs and (iii) patients with missing values because of other reason. The last mentioned analyses will only be done for strata of at least 200 patient (overall and for each treatment group).

Number and percentage of patients within the different adherence classes will be displayed for dabigatran etexilate and VKA patients, respectively. Furthermore the following subgroups will be presented for adherence (overall and for each treatment group):

- CHA₂DS₂-VASc-Score (<2, ≥2)
- Age (<65, 65- <75, ≥75)
- Previous stroke Yes, No)
- Medical specialty of attending physician (Internist, Cardiologist, General practitioner, Other)
- Daily dose of Pradaxa® at initial visit (2x110mg daily, 2x150mg daily) [Patients treated with Pradaxa® only]
- HAS-BLED-Score (<3, ≥3).

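### SAP 7.4 splits a baseline table by leaving the study where Protocol 7.3 splits it by stopping the drug, and SAP section 4 declares no change

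*SAP*

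**What the plan says.** Protocol 7.3, under persistence and reasons for discontinuation, follows the Cox regression with a descriptive table: "Baseline characteristics will be presented stratified for patients who discontinue the treatment in the course of the study and those who do not".

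SAP 7.4 has its counterpart at the same point: "Baseline characteristics will be presented stratified by patients who discontinued the study prematurely versus no discontinuation".

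SAP section 3 states that "the TSAP is based on the planned analysis specification as written in CTP Section 7". The section headed "4. CHANGES IN THE PLANNED ANALYSIS OF THE STUDY" contains a single word, to the effect that there are none.

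Both documents keep the two events apart elsewhere:

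- In SAP 7.4, patients who leave the "study prematurely and without documented treatment discontinuation will be censored at study termination". Protocol 7.3 has the same rule. A treatment stop is the persistence event.
- SAP 7.5 divides patients without a Morisky score into "(i) the groups of study drop-outs, (ii) treatment drop-outs and (iii) patients with missing values because of other reason".
- Protocol 7.3, on adherence, likewise names two groups: "Patients who at the time of the visit are no longer on the initial therapy and those who have already discontinued the study".

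**The concern.** The primary objective is persistence, and the protocol planned this table to show how patients who stop the drug differ at baseline from those who continue. A programmer working from the final SAP would use a different variable, study exit, and would have no signal that the protocol asked for something else. The output could then be reported as a profile of non-persistent patients when it is not one.

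**Working it through.** **Are both texts current?** Yes. Local Amendment 1 changes the front page, the synopsis and the sample-size section. Local Amendment 2 changes the front page and the synopsis. Neither touches the planned analyses in Protocol 7.3.

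**Does another SAP output supply the protocol's table?** No.

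- SAP 7.5 tabulates numbers and reasons for stopping, without baseline characteristics.
- Its baseline comparison of drop-outs concerns missing Morisky scores at 6 months. It uses patients with an evaluable score as the reference, and it runs only for strata of at least 200.
- The Cox models and subgroups in SAP 7.4 cover a short list of factors, not the full set of baseline variables.

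**What would the SAP table contain?** That depends on whether stoppers stay under observation, and the documents point both ways.

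- The synopsis says "all enrolled AF patients will be observed over 12 months during treatment with dabigatran etexilate or VKA", and Protocol 5.2.2.2 ends adverse event collection 30 days after a premature stop. Both lean towards stoppers leaving.
- The adherence text in Protocol 7.3 and SAP 7.5 separates patients off the initial therapy at 6 months from those already out of the study. This leans towards at least some stoppers staying.

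If stoppers leave, the discontinued group merges them with patients censored without a documented stop. If they stay, that group omits them.

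**Illustrative sizes.** The inputs come from Local Amendment 1, change 3: 800 patients per group, 66% matched, 15% drop-outs and missing values combined, persistence 63% for dabigatran and 51, 53.8 or 56.5% for VKA. The plan's matched total reproduces: 2 × 800 × 0.66 = 1056, or 528 per group. The whole 15% is taken as study exits, independent of stopping.

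*Reading A: 15% is a net annual exit rate, with constant hazards.* For persistence p, λ = −ln p and μ = −ln 0.85 = 0.1625.

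- Stops per group = 528 × λ/(λ+μ) × (1 − 0.85p)
- Exits without a stop = 528 × μ/(λ+μ) × (1 − 0.85p)
- Dabigatran: 528 × 0.7398 × 0.4645 = 181 stops; 528 × 0.2602 × 0.4645 = 64 exits
- VKA at 51%: 528 × 0.8056 × 0.5665 = 241 stops; 58 exits

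*Reading B: 15% of patients are observed to leave without a documented stop.*

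- Exits = 0.15 × 1056 = 158.4
- Stops = 0.85 × 528 × [(1 − 0.63) + (1 − VKA rate)], for example 448.8 × 0.86 = 386.0 at 51%

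| VKA persistence | Reading | Stoppers | Leavers, no stop | Merged | Leavers' share |
|---|---|---|---|---|---|
| 51% | A | 422.4 | 122.0 | 544.4 | 22% |
| 51% | B | 386.0 | 158.4 | 544.4 | 29% |
| 53.8% | A | 408.5 | 123.3 | 531.8 | 23% |
| 53.8% | B | 373.4 | 158.4 | 531.8 | 30% |
| 56.5% | A | 395.1 | 124.6 | 519.7 | 24% |
| 56.5% | B | 361.3 | 158.4 | 519.7 | 30% |

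The merged total is the same under both readings because each group contributes 528 × (1 − 0.85p). If every stopper stayed under observation, the discontinued group would hold only the 122 to 158 leavers and none of the 361 to 422 stoppers.

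**The case against.** The strongest reply is that this is a slip. The sentence sits exactly where the protocol has its treatment-stop sentence, the SAP's English is loose in places, and an unintended wording error would not appear in a list of changes. That may well be so, and the documents do not show a deliberate change of analysis. But the SAP is final and both documents give the two terms different meanings, so the text needs correcting whatever its origin.

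A second reply is that much of the content survives. SAP 7.4 still plans univariate Cox models and persistence by stroke score, bleeding score, age, previous stroke, physician specialty and dabigatran dose, and SAP 7.5 still gives counts and reasons for stopping. This stands, and it limits the loss to the side-by-side description of the remaining baseline variables, such as education, comorbidity and co-medication.

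A reader might also infer that stoppers who stay under observation would be counted in the no-discontinuation group. The SAP does not say so. Its comparator is unqualified, and such a patient could equally fit neither group.

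Finally, the sizes span a wide range and rest on assumptions. That is accepted. The conflict is one of wording and does not depend on them.

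**Conclusion.** The discrepancy holds: the two current documents define the same table by different events, and the SAP declares no change. Read as written, the SAP table is not the protocol's profile of patients who stop the drug.

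The actual size is undetermined because the documents do not say how many stoppers remain under observation. As illustration only, leavers without a documented stop would be about 22 to 30% of the discontinued group if all stoppers leave. That assumes the planning persistence rates hold, exits are independent of stops, and the whole 15% is study exit; the share is smaller if part of the 15% is missing values.

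A reader might infer that the persistence comparison itself is compromised. The documents do not support that: the Kaplan-Meier, log-rank, Cox, subgroup and reasons outputs are all defined on treatment stop. The effect is confined to one descriptive table in an exploratory study. It should be corrected, but it does not threaten the main result.

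**What to change.** In SAP 7.4, restore the protocol's split, by treatment discontinuation during the study against none. That is the whole correction needed for consistency with Protocol 7.3.

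Two additions are optional. Patients who left without a documented stop could be shown separately, since their persistence status at 12 months is unknown; this goes beyond the protocol's two groups, and the column may hold few patients. A split by study exit could be kept as an extra table. Either addition should be declared in SAP section 4.

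The cost is one wording change and, if wanted, one column or table. It needs no new data and no new model.

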7.1 Statistical design model

This is a non-randomised, open, multicentre, non-interventional cohort study with patients who are suffering from non-valvular atrial fibrillation and have recently been prescribed an oral anticoagulant (VKA or dabigatran etexilate). As the treatment is attributed by the doctor, differences in patient characteristics between the two patient groups receiving VKA or dabigatran treatment that are to be compared may be expected. To improve the comparability of the treatment groups and hence increase the internal validity, the analysis of the primary target variable (persistence) is planned using methods such as matching or trimming of the population and adjustment.

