7. PLANNED ANALYSIS

All analyses in this study are descriptive; results are to be interpreted in an explorative manner.

For categorical variables summary tabulations of the number and percentage within each category (with a category for missing data) of the parameter will be presented. For continuous variables N, mean, SD, minimum, median, maximum and number of missing values will be presented. To achieve a valid comparability of compliance (persistence and adherence) patients prescribed to dabigatran etexilate or VKA will be matched 1:1 based on the Exposure Propensity Score (PS) and caliper matching with caliper of width equal to 0.2xStandard deviation of PS.

The Propensity Score will be calculated based on a logistic regression model taking the choice of treatment as dependent variable and baseline characteristics as independent variables into account. All baseline variables with an a priori association to persistence and adherence will be included into the regression analysis.

These variables correspond to the potential cofounder variables for a comparative analysis.

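### The only sensitivity analysis of the persistence comparison adjusts for the same four covariates as the matching, so it checks the matching but not confounding by anything outside that list

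*SAP*

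**What the plan says.** Protocol 7.1 recognises the basic problem: "As the treatment is attributed by the doctor, differences in patient characteristics between the two patient groups" are to be expected. SAP 7 answers it with matching: "To achieve a valid comparability of compliance (persistence and adherence) patients prescribed to dabigatran etexilate or VKA will be matched 1:1". SAP 7.4 then makes the matched cohort the basis of the primary result: "The analysis of the primary endpoint will be based on the patient cohort resulting from the 1:1 matching".

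The check on that result is a multivariate Cox model ("including factors for the calculation of the propensity score and the choice of treatment) will be used as sensitivity analysis"), run on patients in the trimmed common support of the propensity score ("instead of the matched pairs), will be included in this analysis"). Protocol 7.3 defines it the same way. SAP 7.4 gives a single list for both purposes: "The following covariates will be used –depending on the sample size- for the Propensity Score Matching and the sensitivity analysis". The list holds CHA2DS2-VASc (<2, ≥2), HAS-BLED (<3, ≥3), age in three classes and previous stroke. The one entry marked "sensitivity analysis only" is treatment, which is the exposure and not a confounder.

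No other sensitivity analysis of persistence is planned. The one in SAP 7.5 concerns unanswered Morisky items.

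**The concern.** A sensitivity analysis tests an assumption only if it relaxes it. The assumption most open to doubt in a non-randomised comparison is that nothing outside the adjustment set drives both the choice of drug and stopping it. The matched analysis and the Cox model share that assumption because they share the adjustment set.

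The protocol itself gives reason to doubt it. Section 2.1 lists socioeconomic status, personal convictions, symptom severity, frequency of intake and side effects among the reasons for poor compliance. None of these is in the list. Protocol 7.3 and SAP 7 both state that every baseline variable with an a priori association with persistence or adherence goes into the propensity model. Section 6.2 collects sex, education, marital status, insurance status, number and daily frequency of other medicines, and comorbidities at Visit 1.

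At stake is how agreement between the two hazard ratios is read. Agreement would show that the result does not hinge on the matching. It would carry no information about confounders outside the list.

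**Working it through.** **1. The two adjustment sets (SAP 7.4).**

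| | Matched analysis | Sensitivity Cox model |
|---|---|---|
| Confounders | CHA2DS2-VASc, HAS-BLED, age, stroke | the same four, same cut-points |
| Patients | matched pairs | common support after 2.5%/97.5% trimming in each arm |
| Method | pair-stratified log-rank | regression |

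Population and method differ. The variables controlled do not.

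**2. How much the regression can still correct on the four factors.** The categories give 2 × 2 × 3 × 2 = 24 patterns. Taking age 75 or over and a previous stroke each to put CHA2DS2-VASc at 2 or more, 8 patterns with a score below 2 cannot occur, which leaves 16. In simulation B below, the propensity score took 16 values and about 98% of pairs had exactly equal scores. Almost no imbalance on the four factors remains after matching.

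**3. What an omitted factor does.** Both simulations start from 800 per arm, 15% drop-out and a true treatment hazard ratio (HR) of 1. Confounder strengths and covariate prevalences are assumptions; no document gives them.

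| Omitted factor (assumed) | Matched HR | Sensitivity HR | Factor added to model |
|---|---|---|---|
| A: prevalence 60% vs 45%, halves the hazard of stopping | 0.900 | 0.899 | 0.998 |
| B: odds ratio 1.5 with drug, HR 1.5 with stopping | 1.03 | 1.03 | 0.99 |
| B: 2 and 1.5 | 1.07 | 1.07 | 1.00 |
| B: 2 and 2 | 1.13 | 1.13 | 1.00 |
| B: none | 0.99 | 0.99 | 0.99 |

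A used 200 simulated studies and B 120 per row. A hand check of A, by the usual approximation for an omitted binary factor: (1 + 0.60 × (0.5 − 1)) / (1 + 0.45 × (0.5 − 1)) = 0.70/0.775 = 0.903.

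In A, p ≤ 0.05 occurred in 21% of matched analyses and 26.5% of sensitivity analyses (Monte Carlo error about 3 points each), against about 5 to 6% without the factor. In B, the two log hazard ratios correlated 0.94 to 0.97 across runs.

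**4. Comparison with the planned effects.** Inputs from Protocol 7.5 as changed by Local Amendment 1: persistence 63% on dabigatran; 51%, 53.8% or 56.5% on VKA; 15% drop-out; matched N = 2 × 0.66 × 800 = 1056, which agrees with the stated figure.

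- HR = ln(0.63)/ln(S_VKA), assuming exponential times.
- Events = 528 × (d1 + d2), where d = λ/(λ + ε) × (1 − S × 0.85), λ = −ln S, ε = −ln 0.85.
- Standard error of log HR ≈ 2/√events, ignoring pair stratification.
- E-value = R + √(R(R − 1)), where 1/R = (1 − 0.5^√HR)/(1 − 0.5^√(1/HR)), the conversion for common outcomes.

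| VKA persistence | HR | Events | Upper 95% limit | E-value, HR | E-value, limit |
|---|---|---|---|---|---|
| 51% | 0.686 | 422 | 0.830 | 1.92 | 1.53 |
| 53.8% | 0.745 | 409 | 0.905 | 1.75 | 1.35 |
| 56.5% | 0.809 | 395 | 0.986 | 1.59 | 1.11 |

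A shift to 0.90 is ln(0.90)/ln(HR) = 28%, 36% and 50% of these log hazard ratios. It would not explain the planned estimates. Dividing the upper limits by 0.90 gives 0.92, 1.01 and 1.10, so in the second and third rows the interval would no longer exclude 1.

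**5. Room for a larger model.** In 1600 patients at 63% and 53.8%, events are 800 × (0.344 + 0.430) ≈ 619. With about 20 parameters (an assumption, since category counts for education and similar items are not given), that is about 31 events per parameter.

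**The case against.** **The planned Cox model has a real purpose.** It uses patients the matching discards, and the plan expects only 66% of VKA patients to find a partner. A reader might infer that it cannot disagree with the matched result. That is not so: population, trimming and method differ. In a rough run of 100 studies per setting with assumed prevalences, the standard deviation of the difference in log hazard ratios was 0.028 with about 89% matched and about 0.057 with about 60% matched, where the correlation was 0.81. The mean hazard ratios still agreed, so the shared bias remains.

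**Other analyses touch on confounding.** A reader might infer that it goes wholly unexamined. SAP 7.1 and 7.2 tabulate baseline characteristics, comorbidities and medication in the matched cohort, so imbalance in collected items will be visible. These tables feed no effect estimate. The association Cox model in SAP 7.4 adds only physician specialty, and its stepwise selection (stay level 0.1) is not said to protect treatment from removal.

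**Some omitted items are partly covered.** Sex and several comorbidities are components of CHA2DS2-VASc. They enter only through whether the total reaches 2.

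**Everything is exploratory.** True, and it lessens the weight of the false-significance rates. It does not lessen bias in the estimate, and comparing persistence is the primary objective.

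**Some confounders cannot be adjusted for.** Expected compliance and patient preference are not among the Visit 1 items. This stands: an added model helps only with collected variables.

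**Conclusion.** The point holds. The matched analysis and its only sensitivity analysis control the same four categorised covariates, so their agreement supports robustness to matching, trimming and method and to nothing else. This follows from the text of SAP 7.4 and needs no simulation.

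The size is uncertain. With the strengths assumed above, null hazard ratios moved to 0.90 in one simulation and to between 1.03 and 1.13 in the other, almost equally in both analyses. The documents do not support the inference that a confounder of this size would account for the planned effects of 0.69 to 0.81. It would take up 28% to 50% of them on the log scale. Nor do they say that agreement will be presented as evidence against unmeasured confounding; the risk is that it is read so. The change is worth making because bias from items already collected can be reduced at little cost.

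**What to change.** In SAP 7.4:

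1. Keep the planned Cox model and describe it as the check on dependence on matching.
2. Add a second sensitivity Cox model with treatment forced in. Besides the four matching covariates it contains prespecified baseline items already collected: sex, education, marital and insurance status, number and daily frequency of other medicines, comorbidities, and physician specialty.
3. Report an E-value for the treatment hazard ratio and for its confidence limit nearest 1, to cover factors that are not collected.

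In SAP 7, replace the general claim of valid comparability by balance on the matched variables. State that agreement of the matched result with the planned Cox model does not bear on other confounders.

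The cost is SAP wording, one extra model and one line of output, with no new data. The downside is that a few patients with a missing added covariate drop out of the second model, since no imputation is planned.
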